5.4 Use of radiation: *N/A*

5.5 Use of Center for Magnetic Resonance Research: *N/A*

6.0 Data and Specimen Banking

6.1 Storage and Access: Urine will be collected from subjects at the baseline and week 6. The samples will be stored in freezers located in labs used by faculty in the ECP department (currently these freezers are located on the 5th floor of [name]).

6.2 Data: Urine samples will be labeled with subject number and date of visit. Samples will be assayed for cotinine concentrations. Cotinine is a metabolite of nicotine and frequently used to confirm abstinence or quantify nicotine exposure. Urine may also in the future be used to assay other measures related to smoking or specifically related to smoking menthol cigarettes or substances related to e-cigarette use. Examples of such measures would include assaying nicotine or metabolites of nicotine other than cotinine, assaying menthol concentrations or

assaying toxicants associated with smoking to determine if exposure to such substances changes when smokers use e-cigarettes or if flavor of e-cigarettes affects these measures.

6.3 The current planned analyses will be performed by labs within the University of Minnesota. However, if by the time the samples are collected these labs are no longer able to provide this service, these samples may be sent elsewhere for analysis. Similarly, if samples are in the future assayed for other measures, they may be sent to external laboratories depending on the capabilities and cost of such analyses. If samples for other measures are sent to external laboratories for additional assays, they will be labeled with a subject code that has no identifiable information on it. Prior to sending samples to an outside source, the IRB will be notified.

7.0 Sharing of Results with Participants

7.1 Study results will not be shared with participants.

8.0 Study Duration

1.2.2 The anticipated duration for an individual participant's participation in the study is approximately 6 to 8 weeks (depending in part on length of time between the screening visit and the baseline visit).

2.2.2 Data collection is expected to be complete within 2 year of starting the study.

9.0 Study Population

9.1 Inclusion Criteria: To be eligible subjects must:

- a) Be between the ages of 21 and 64
- b) Smoke (on average) at least 5 cigarettes per day over the past year
- c) Purchase exclusively menthol cigarettes
- d) Not currently motivated to quit smoking
- e) Able to receive daily text or email survey reminders and follow the link provided to complete the online RedCap surveys

9.2 Exclusion Criteria: Subjects will be excluded if they:

- a) Report a serious, unstable medical or psychiatric condition
- b) Have a history of substance abuse (other than nicotine) within 3 months of beginning the study
- c) Use any medications that might interfere with measures to be studied (for example, medications known to affect smoking)

- d) Have used any smoking cessation therapy during the past month
- e) Regularly use any form of tobacco other than cigarettes (> 9 times per month)
- f) Are pregnant or breast feeding or planning to become pregnant or breast feed during the study
- g) Currently participating in other clinical research studies

9.3 Screening: At the screening visit, subjects will complete a series of questionnaires including those that ask about medical history, smoking history, and motivation to quit smoking. All inclusion / exclusion will be based on self-report except for smoking status which will be confirmed via an exhaled carbon monoxide (CO) concentration of ≥ 8 ppm or a urinary nicotine test strip reading of 6. Non-pregnant status will be confirmed via a urine pregnancy test.

10.0 Vulnerable Populations

10.1 Vulnerable Populations:

- Children
- Pregnant women/Fetuses/Neonates
- Prisoners
- Adults lacking capacity to consent and/or adults with diminished capacity to consent, including, but not limited to, those with acute medical conditions, psychiatric disorders, neurologic disorders, developmental disorders, and behavioral disorders
- Approached for participation in research during a stressful situation such as emergency room setting, childbirth (labor), etc.
- Disadvantaged in the distribution of social goods and services such as income, housing, or healthcare
- Serious health condition for which there are no satisfactory standard treatments
- Fear of negative consequences for not participating in the research (e.g. institutionalization, deportation, disclosure of stigmatizing behavior)
- Any other circumstance/dynamic that could increase vulnerability to coercion or exploitation that might influence consent to research or decision to continue in research
- Undervalued or disenfranchised social group
- Members of the military
- Non-English speakers
- Those unable to read (illiterate)
- Employees of the researcher
- Students of the researcher
- None of the above

11.0 Local Number of Participants

11.1 Local Number of Participants to Be Consented: We plan on recruiting approximately 60 subjects anticipating that approximately 54 will complete the study. We expect that as many as 120 subjects will undergo the consent process. Some of those that attend the screening visit will likely not meet inclusion / exclusion criteria whereas others will not be interested in participating.

12.0 Local Recruitment Methods

12.1 Recruitment Process: Advertisements for the study will be placed in various print and on-line sources and via flyers. Interested participants will call the phone number listed. Study staff will explain the study to potential study subjects. Individuals that indicate an interest in participating in the study will then be screened by telephone to see if they are likely to qualify for the study. Additionally subjects that in previous studies agreed to be contacted regarding other research opportunities may be called – in this case, subjects will be informed why they are being called with the telephone screening process being the same as for subjects who contacted us after seeing the study advertised.

12.2 Recruitment Materials: Flyers and advertisements placed in local publications or on on-line resources (for example, Craigslist) will be used to recruit participants.

12.3 Payment: Subjects will be paid as follows: \$20 for completing the screening visit. In addition to receiving credits for tobacco products, they will receive \$15 for each of the subsequent 4 visits in this study. They will receive an additional \$15 at the baseline visit, and week 2, 4, and 6 visits if they have completed at least 85% of their scheduled electronic diary assessments and have brought in their used e-cigarette cartridges. A \$50 bonus will be given to subjects completing the study and all study related assessments. Up to \$190 will therefore be paid to subjects for the entire study. Payment will be provided at the end of each visit in the form of a pre-paid debit card.

13.0 Withdrawal of Participants

13.1 Withdrawal Circumstances: Subjects may be withdrawn from the study if they fail to follow study procedures (e.g., show up to scheduled study visits) or if there are changes to their health that are likely to affect smoking behavior. Additionally, subjects will be told that participation is voluntary and that they may discontinue participation at any time for any reasons.

13.2 Withdrawal Procedures: We will attempt to contact subjects by telephone who do not show up to scheduled visit to ascertain if they wish to continue to participate in the study (and if not, why not) and to determine smoking status at the time of their withdrawal.

14.0 Risks to Participants

14.1 Foreseeable Risks: The tobacco products and medicinal nicotine products that are used for this study are those that are commercially available. Although there are numerous risks associated with smoking cigarettes, we are only enrolling those who are already smoking and are at the time of enrollment not motivated to quit. The risks of continuing to smoke cigarettes within the context of the study are no greater than if they were to continue smoking cigarettes outside of the study.

E-cigarettes do not currently undergo regulatory evaluation, however they are easily available and increasingly being used. The risks of using e-cigarettes are generally thought to be lower to an individual than the risks of smoking. Nicotine gum and lozenge are available without a prescription, commonly used and generally well tolerated. Side effects that can occur include hiccups, mouth or throat irritation and upset stomach.

All of the products being provided to subjects contain nicotine and it is possible that overuse can lead to symptoms of nicotine toxicity which could include nausea, vomiting, dizziness, weakness, and rapid heartbeat. Considering that we only enrolling experienced smokers, nicotine toxicity is not likely.

The e-cigarette liquid contains propylene glycol which may be associated with throat irritation. There have been occasional reports of e-cigarette devices malfunctioning and causing injury to users.

There have been recent reports of seizures and breathing problems occurring in people who use e-cigarettes. These cases are being investigated and at this time it is not known how common these problems are or what is causing them. Since many of the cases of breathing problems occurred in individuals using e-cigarettes products with liquids that contain cannabinoid products such as THC, it is likely that the risk is due to people adding substances to e-liquids that were not intended by the manufacturer. The e-cigarette products available in the study are widely available and widely used. The devices and liquids provided to participants are not modified in any way after purchase.

As with any product, there is a risk that unanticipated effects from using the e-cigarette or lozenges may occur, however the risk of using the product as directed by the manufacturer is no higher than it would be if subjects were to buy and use these products outside of the study.

14.2 Reproduction Risks: Smoking cigarettes during pregnancy is known to be harmful to reproductive health. We will therefore exclude women who are pregnant or are planning to become pregnant during the study. Women who inform us that they have become pregnant during the study will not be provided any additional tobacco / nicotine products.

14.3 Risks to Others: There are no anticipated risks to others.

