4.3 IND/IDE. N/A

4.4 Biosafety: N/A

5.0 Procedures Involved

5.1 Study Design: This is a pilot study in which over a 6 week period, menthol cigarette smokers will receive all of their tobacco products from a simulated experimental marketplace. Smokers will be assigned to one of three marketplace conditions: 1) a condition simulating a ban on menthol cigarettes but not menthol e-cigarettes; 2) a condition simulating a ban on both menthol cigarettes and menthol e-cigarettes; and 3) a condition in which menthol is not banned for either product (i.e., the control condition). All conditions would have medicinal nicotine available if subjects decide to quit tobacco products entirely. Subjects would receive "credits" that they can exchange, at visits occurring every two weeks, for any product available in their randomized marketplace condition. At the end of the experimental period any unused credits can be exchanged for monetary payment.

5.2 Study Procedures: The following procedures will occur during the study.

5.2.1 Screening Visit: Initial eligibility will be assessed via a phone interview or online screening form housed on REDCap. All screened participants will be notified by phone or email regarding their eligibility to be scheduled for a screening visit at which written informed consent will be obtained and eligibility

confirmed. At the screening visit, medical and psychiatric history will be obtained via subject report. Women will have a urine pregnancy test to confirm that they are not pregnant. A medical professional (e.g., Nurse Practitioner) will review medical histories to ensure eligibility. Baseline questionnaires assessing smoking history will be administered and an exhaled carbon monoxide (CO) will be measured to confirm smoking ($CO \geq 8$ ppm). A NicCheck using a urine sample will be performed (with a cut-off = 6 for those who otherwise qualify but for whom CO is < 8 ppm (e.g., they didn't smoke that morning, they came straight from work, etc.). Subjects who qualify and are interested in continuing will be invited to return to the baseline visit.

After eligibility is confirmed, subjects will begin receiving links daily via either text message or email (whichever they prefer) to a tobacco use survey that is to be completed on RedCap. On this survey subjects will report use of all tobacco and nicotine containing products used during the past day. These survey will continue until the end of the subject's participation in the study.

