5.2.2 Baseline Visit (i.e., week 0): At the baseline visit, urine will be collected from which baseline urinary cotinine concentrations will be measured. Exhaled CO will be measured from a breath sample. Tobacco use behavior subsequent to the screening visit will be determined as will subjects' level of craving, withdrawal, motivation and self-efficacy to quit smoking and support for a ban on a variety of menthol containing tobacco products. Degree of nicotine dependence will be assessed using the Fagerstrom Test for Nicotine Dependence.³⁰ Subjects will be informed which products are available in the marketplace that they have been randomized to and will be allowed to handle each of the products and examine the packaging that each normally comes in.

Subject will be given credits at each visit that can be exchanged for products in their marketplace. All products will be discounted to approximately 66% of the retail market value (similar to the study summarized in preliminary data) in order to discourage subjects from purchasing products outside the marketplace and also prevent hoarding credits for payment at the end of the study. The credit amount will be calculated in order to allow on average a 1 pack/day smoker to replace all of their tobacco products based on normal usage patterns (e.g., for example, one cartridge of Vuse lasts about as long as one pack of cigarette). In order to discourage subjects obtaining more products than they need, any credits not used at each visit can be banked and used at later visits or converted to monetary payment at the end of the study. Subjects will be informed that they can obtain any amount or type of product up to the value of current and banked credits and will be provided with the packaging that normally accompanies these products. Instructions for product use will be primarily limited to what is on the packaging so as to more accurately simulate natural marketplace conditions; however subjects can ask questions about the products to which accurate answers will be provided. While subjects will be encouraged to obtain all tobacco products they use from the experimental marketplace, no penalties will be levied for outside purchases in order to encourage truthful reports of noncompliance.

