5.2.3 Evaluation Visits (3 visits occurring at 2 week intervals). Subsequent to the baseline visit, subjects will be evaluated at 3 visits occurring at two week intervals (i.e., at approximately 2, 4 and 6 weeks after the baseline visit). To each visit, subjects will be asked to bring back any unused product as well as all used and unused e-cigarette cartridges or e-fluid vials. The cartridges and vials will be weighed prior to distribution and after use to determine the extent to which they were used. Participants will be allowed to keep any of the unused products so as to not discourage them from bringing back unused product.

At each visit, exhaled carbon monoxide concentrations will be measured and subjects will complete questionnaires assessing various aspects of smoking behavior including craving, withdrawal symptoms and motivation to quit smoking. Questionnaires assessing how they rate the effects of the products they are using and their perceived health risks of using these products will also be assessed. A food diary asking primarily about dietary menthol will be completed to determine if dietary intake changes occur if menthol in tobacco products is no longer available. Level of support for a ban on a variety of menthol containing tobacco products will be evaluated at the baseline and week 6 visits.

Additionally, at the week 6 visit urine will be collected in order to measure cotinine concentrations. At each visit (except for the week 6 visit), subjects will again have the opportunity to obtain additional products for the subsequent 2 weeks using their available credits. They may choose to obtain any of the available products in their marketplace and are not limited to products that they had previously chosen.

5.3 Individually Identifiable Health Information: All information is collected directly from subjects (i.e., medical records will not be requested) and this is not a treatment study. The data being collected therefore does not meet the definition of PHI.

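### After the single screening test, no listed procedure asks about pregnancy before products are exchanged at weeks 0, 2 and 4, so the stop-supply rule in section 14.2 depends on a woman volunteering it

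*Combined protocol and SAP*

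**What the plan says.** All references are to the combined protocol and SAP.

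- **Entry.** Section 9.2 (f) excludes women who are pregnant or plan to become so during the study. At the screening visit (5.2.1), "Women will have a urine pregnancy test to confirm that they are not pregnant". Section 9.3 repeats this as part of screening. No later test is listed.
- **Supply.** At baseline (5.2.2), "Subject will be given credits at each visit that can be exchanged for products in their marketplace". At the evaluation visits other than week 6 (5.2.3), "subjects will again have the opportunity to obtain additional products for the subsequent 2 weeks using their available credits". Products are therefore handed over at weeks 0, 2 and 4.
- **What is asked along the way.** At weeks 2, 4 and 6, "subjects will complete questionnaires assessing various aspects of smoking behavior including craving, withdrawal symptoms and motivation to quit smoking". For the daily survey (5.2.1), "On this survey subjects will report use of all tobacco and nicotine containing products used during the past day".
- **Stop rule.** Section 14.2: "Women who inform us that they have become pregnant during the study will not be provided any additional tobacco / nicotine products".

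**The concern.** Section 14.2 recognises that smoking in pregnancy is harmful and commits the study not to go on supplying a pregnant participant. A rule of this kind needs a step that sets it off. Here the trigger is the woman informing the study, and nothing in the listed procedures prompts her to do so at the moment when it matters, just before products are handed over.

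Excluding women who plan a pregnancy does not rule out an unplanned one, and a single negative test says nothing about conception after it. Disclosure also ends access to products that 5.2.2 prices at roughly two thirds of retail, so a woman has some reason not to raise the subject unprompted.

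What is at stake is whether the study carries out its own safety intention. A woman who knows that she is pregnant could receive more cigarettes, e-cigarettes or nicotine products because nobody asked. The scientific results are not at stake.

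**Working it through.** The plan gives no figure on this point to reproduce. The check is a reading of every listed procedure, plus simple timing.

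**Step 1. Time from the test to each exchange.** Section 8.0 puts individual participation at about 6 to 8 weeks, "depending in part on length of time between the screening visit and the baseline visit". Section 5.1 sets a 6-week marketplace period.

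- Screening to baseline = (6 to 8) − 6 = about 0 to 2 weeks.
- Time from test to exchange = that gap + the visit week.

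| Exchange | Calculation | Weeks since the only listed test |
|---|---|---|
| Week 0 | (0 to 2) + 0 | about 0-2 |
| Week 2 | (0 to 2) + 2 | about 2-4 |
| Week 4 | (0 to 2) + 4 | about 4-6 |

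**Step 2. Search for a trigger.**

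| Place | What is listed | Pregnancy question or test? |
|---|---|---|
| 5.2.1, 9.3 screening | Medical history, urine pregnancy test | Yes, once |
| 5.2.1 daily survey | Tobacco and nicotine use | No |
| 5.2.2 week 0 | Urine for cotinine, CO, tobacco use, craving, withdrawal, motivation and self-efficacy, ban support, dependence score | No |
| 5.2.3 weeks 2, 4, 6 | Returned product, CO, smoking questionnaires, product ratings, perceived risk, food diary; at week 6 also ban support and urine cotinine | No |
| 13.1 withdrawal | Permits withdrawal when a health change could alter smoking | No |
| 18.0 monitoring | Team meetings at least every two weeks, with adverse event review | No |

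Exchanges preceded by a listed pregnancy question: 0 of 3 now, 3 of 3 with the change proposed below.

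**Step 3. What a question could achieve.** Take a woman who knows that she is pregnant, would not volunteer it, but would answer truthfully if asked. The number of exchanges stopped depends on when she learns:

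- before week 0: 3 (weeks 0, 2 and 4)
- between weeks 0 and 2: 2 (weeks 2 and 4)
- between weeks 2 and 4: 1 (week 4)
- after week 4: 0, because no exchange remains

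This is a count per such woman. The documents give neither the number of women to be enrolled nor a pregnancy rate, so no expected total is calculated.

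**The case against.** The strongest reply is that the plan already has three layers (an entry exclusion, a urine test and a stop rule) and that a fourth may exist out of sight. The consent pages are not in the file and are a natural place to tell women to report a pregnancy. The questionnaire lists in 5.2.2 and 5.2.3 are not presented as complete. The adverse event review in 18.0 presupposes some collection of events, at about the same interval as the visits. This stands as a limit: a reader might infer that participants are never told to report a pregnancy, and the documents do not support that. What remains is narrower. No listed procedure puts the question to a participant before an exchange, and a consent instruction given weeks earlier would still leave it to her to come forward.

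The second reply is that the benefit reaches very few people. It needs an unplanned conception, known by week 4, not volunteered, yet truthfully admitted when asked. Among the women in a trial of about 60 participants, that is likely to be a very small number. This stands too, and it sets the priority.

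The third reply is that harm is not shown. Participants already smoke and can buy outside the study; 14.1 and 18.0 argue that the risk is no greater than that. Stopping supply also withdraws e-cigarettes and nicotine gum or lozenge while shop cigarettes remain available. This is fair as to net exposure. It does not answer the point that the study has itself decided, in 14.2, not to be the supplier.

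A reader might also be tempted to turn the missed exchanges into an amount of product, using the credit level in 5.2.2, which is set to "allow on average a 1 pack/day smoker to replace all of their tobacco products". That would not hold. Unused credits can be banked and spent at a later visit, so one exchange can exceed one visit's allotment. They can also be converted to cash, so an exchange can be smaller. The same section therefore gives no ceiling per exchange and no expected use.

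**Conclusion.** The point holds in a limited form. Pregnancy is tested once; three product exchanges follow, the last about 4 to 6 weeks after the test; and no listed step asks about pregnancy before any of them. As written, the rule in 14.2 rests on disclosure that nothing listed prompts.

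It should not be read as more than that. A reader might infer that the protocol breaches its own rule or prevents staff from asking. It does neither: the wording of 14.2 is also satisfied when a woman answers a staff question. Nothing listed requires the question to be put.

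The size is small. Per affected woman, one to three exchanges could be stopped if she learns before week 4, and none after. The number of such women cannot be estimated from the documents and is likely to be very small. No endpoint, sample size or analysis is affected. The conclusion rests on two assumptions: that the procedures listed in 5.2 are substantially what is done at visits, and that some women who would not volunteer a pregnancy would acknowledge it when asked. It is a low-priority safety improvement, worth making because it is nearly free.

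**What to change.** In 5.2.2 and 5.2.3 add: *Before each product exchange (weeks 0, 2 and 4), women of childbearing potential will be asked whether they are or may be pregnant; if unsure, a urine pregnancy test will be done before products are provided.*

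Reword 14.2 to match: *If a pregnancy is identified by this question or reported in any other way, no further tobacco or nicotine products will be supplied.*

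If the consent form already asks women to report a pregnancy, keep that instruction; the two work together. There is no need to extend the repeated question to breast-feeding. After a negative screening test, newly starting to breast-feed within a 6 to 8 week study is practically excluded.

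The cost is a minute or so per visit, one line on the visit form and an occasional test strip. Urine is already collected at week 0; at weeks 2 and 4 a sample would be needed only when a woman is unsure. The remaining weakness is that a prompted answer will still miss pregnancies that are unrecognised, or that a woman conceals because disclosure ends her supply.
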